Study Protocol w/ Statistical Analysis Plan

Last Updated 10/17/2022

IRB

1) Protocol Title

Optimizing After Visit Instructions in an Outpatient Academic Rheumatology Clinic: A Prospective Randomized Open Label Trial

2) Objectives

The aim of this study is to assess the quality of standardized after visit instructions (AVI) and patient teach back in an outpatient academic rheumatology clinic by measuring patient retention of disease management and overall patient satisfaction. We propose a prospective randomized open label trial to determine if the presence of optimized and standardized discharge processes lead to better comprehension and retention of a patient's management plan.

Primary outcome will be level of retention based on the Follow-up Telephone Protocol.

Secondary outcomes assessed will include level of patient satisfaction based on our Post visit Survey and after visit instructions meeting patients' health literacy levels measured from the REALM-A.

3) Background

Patient education is an essential aspect of administering high quality care. How well patients understand their diagnoses and implement their plan of care is based on a multitude of factors that can drastically impact disease outcomes.^{1,2} One of the key social determinants that affects a patients ability to comprehend and act on their medical conditions is health literacy (HL). The Center for Disease Control (CDC) defines two different types of HL in their updated Healthy People 2030 initiative. Personal HL is "the degree to which individuals have the ability to find, understand, and use information and services to inform health-related decisions and actions for themselves and others". Organizational HL is "the degree to which organizations equitably enable individuals to find, understand, and use information and services to inform health-related decisions and action for themselves and others". These new definitions of HL now acknowledge that organizations have a responsibility, from a public health perspective, to address HL and optimize their approach to varying levels of personal HL.³

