In 2003 the National Assessment of Adult Literacy (NAAL) preformed a large-scale survey of both literacy and HL. It showed that 36% of adults had basic or below basic HL skills. Of the patients that had the lowest health literacy they tended to be older than 65 years old, hispanic or black, male, less than a high school education, and at or below the poverty line.⁴ Low HL has been linked to poor health outcomes including in rheumatic diseases such as rheumatoid arthritis (RA) and systemic lupus erythematosus (SLE).^{5,6} Various studies have been performed assessing literacy rates in rheumatology clinics utilizing the tool, the Rapid Estimate of Adult Literacy in Medicine (REALM). These studies have shown that a range of 10.3% to 19% of patients, within rheumatology clinics, have less than a 9th grade reading level.⁷⁻⁹ Various strategies have been implemented to address the need for improving patients understanding of their medical conditions and management. The American Medical Association and the National Institute of Health have recommended that medical information be written at a 6th grade level.¹⁰ However a recent study looking at the medical information sheets for common rheumatologic drugs from prominent rheumatology organizations in Canada, the UK, and Australia, consistently showed readability scores higher than the 9th

IRB

grade level.¹¹ The “teach-back” (TB) method, where patients repeat in their own words, instructions from the provider is a strategy used to bridge gaps in health literacy. In the emergency room setting TB has been shown to lead to less revisits and better retention of instructions.¹² Teach back communication in rheumatology clinics has been shown to improve overall medication compliance.¹³ In the emergency room setting studies have shown that simplified and standardized after visit instructions can help increase patients overall understanding of their ER visit.¹⁴

An initial retrospective study showed us that written AVI were an underutilized resource in the Rush University Medical Center Rheumatology Clinic (RUMCRC). This retrospective assessment also showed that patients with more medications, higher comorbidity, and learning preferences that favor written AVI, did not receive more AVI.

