For this study we seek to implement various strategies in an academic outpatient rheumatology setting that will address gaps in health literacy. These will include simple, standardized discharge instruction and patient teach back. With these strategies implemented, we will assess patients' retention of knowledge and comprehension of medical instructions. We will also determine the feasibility of implementing these strategies in a rheumatology clinic in terms of time. Long-term studies will analyze how these interventions may have impacted various health related outcomes and patient reported outcomes.

4) Inclusion/Exclusion Criteria

Inclusion Criteria

- Age > 18 yo
- Patients seen in the RUMCRC

Exclusion Criteria

- Tele-medicine visits
- English is not the primary language. This is due to inability of all providers to provide custom AVI due to language limitations

5) Procedures Involved

There will be three cohorts in total: the control group, the standardized AVI only group, and the standardized AVI with teach back group. The control group will involve patients receiving the current standard discharge process at the RUMCRC. The standardized AVI only group will involve patients receiving written standardized AVI that the patients will take home. The standardized AVI with teach back group will include standardized written AVI with the patient repeating to the provider which changes, and future management had been agreed upon during the visit. The standardized AVI will include a text template that providers will use to write customized after visit instructions for the patient that will be in addition to the after-visit summary.

Providers will be taught the standardized discharge approach through in-person education modules and handouts. This education will encompass a 30 minute didactic going over the tenants of the standardized AVI, accessing standardized AVI templates on EMR, and how

IRB

to perform appropriate teach back with patients. No providers that are implementing the intervention will be a part of the research team.

Patients will be randomized before the office visit. Patients will not be told which group they are in unless they explicitly ask. Providers will be told which intervention group a patient is a part of. If a patient is in the control group the providers will not be informed as to not impact behavior. Because of the randomization we believe confounding variables will be distributed equally throughout the groups.

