All patients included in the prospective study will complete an arthritis adapted REALM (REALM-A) form at the observed visit to evaluate their health literacy level. All patients included in the prospective study will also complete an immediate post appointment questionnaire (Post Visit Satisfaction Survey) that will allow them to provide feedback, rate visit satisfaction, and evaluate how after visit instructions were implemented during the visit.

Within 1-2 weeks after the patient's initial visit, a standardized phone call will be performed where patients will be asked specific questions pertaining to their visit in terms of diagnosis, medications, plan, and follow-up appointments. We will score whether their understanding of their disease and management corresponds with what was discussed at the prior visit. This will be performed for all groups. This score will be assessed as our primary outcome.

Baseline data points will be collected for patients in both cohorts including: Basic demographics, new patients versus follow-up visit, MD-HAQ scores, REALM-A score, rheumatologic diagnosis, medications, Charleson co-morbidity scores, barriers to learning, and patient preferences for learning.

After the study, AVI provided will be assessed using Flesch-Kincaid Readability Scores and Grade levels to see how they correspond to patients baseline literacy.

6) Data Management

Summary tables (descriptive statistics and/or frequency tables) will be provided for all variables. Continuous variables will be summarized with descriptive statistics (n, mean, standard deviation, range, and median). Ninety-five (95) percent confidence intervals may also be presented, as appropriate.

Frequency counts and average will be provided for categorical data.

Data will be coded when stored for analysis. Data that is obtained for this study will be coded when stored for analysis. This data will be held under password locked computers that can only be accessed by persons who have approval for access via the IRB. Those that have access to the coded data will require a key to interpret the data. All data will be deleted at the completion of the study.

7) Risks/Benefits

Given the nature of intervention there is little to no risk in terms of patient outcomes. This study will collect private, identifiable information about human subjects. The main risk is to

IRB

subjects' confidentiality should an individual outside of the study team access the study data.

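### Does scoring literacy match only on the written instructions actually provided undermine this secondary outcome?

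*Combined protocol and SAP*

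**What the plan says.** Section 2 (Objectives) names three outcomes: retention on the follow-up telephone call (primary), satisfaction, and whether AVI meet patients' "health literacy levels measured from the REALM-A". The last is measured in Section 5 (Procedures Involved): "After the study, AVI provided will be assessed using Flesch-Kincaid Readability Scores and Grade levels to see how they correspond to patients baseline literacy".

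The arms differ by design in who holds a written AVI. In Section 5, "The control group will involve patients receiving the current standard discharge process at the RUMCRC", whereas "The standardized AVI only group will involve patients receiving written standardized AVI that the patients will take home"; the teach-back arm also receives the written AVI. The standardized AVI is a "text template that providers will use to write customized after visit instructions for the patient that will be in addition to the after-visit summary", so it is described as separate from that summary. Patients are randomised before the visit, and providers are not told who is a control.

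Section 3 (Background) reports from a retrospective study that "written AVI were an underutilized resource" in this clinic, without a rate, and that "patients with more medications, higher comorbidity, and learning preferences that favor written AVI, did not receive more AVI".

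Section 6 (Data Management) promises summary tables for all variables. It writes no between-arm test for the literacy-match outcome and no rule for a patient who received no AVI.

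**The concern.** A patient with no written AVI has no Flesch-Kincaid grade. Nearly all intervention patients should have one; among controls an unknown share will not. Receipt among controls is a provider's choice made after randomisation, so controls with a scored AVI are a selected group. Section 5 relies on randomisation to balance confounders, but that balance holds for everyone randomised and not for the subset with a document to score.

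Because this is a named secondary outcome of a randomised trial, a reader who sees a difference by arm may credit it to the template. The difference could instead reflect which controls were given AVI, or which providers wrote them, and a real difference could be hidden in the same way. Without counts, the reader would not know what share of controls the figure describes.

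**Working it through.** The plan gives no figure to reproduce. It states no sample size, no rate of AVI use in usual care, and no rule for when a Flesch-Kincaid grade matches a REALM-A level. The check is therefore a reading of the text, followed by illustrations.

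**1. What is planned.** Section 5 asks how the documents provided correspond to the literacy of the people who received them. REALM-A is completed by all patients, so each AVI provided can be paired with its reader. The question is answerable among AVI provided. Where there is no document, readability is undefined rather than unobserved, so no other scoring rule would recover it.

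**2. Coverage.** If a fraction r of controls receives an AVI, 1 − r have no value. For assumed r = 0.20, 0.40 and 0.60 this is 80%, 60% and 40%.

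**3. Selection on literacy, with identical writing in all arms.** Let q be the low-literacy share. Section 3 cites "10.3% to 19% of patients, within rheumatology clinics, have less than a 9th grade reading level" from earlier studies, giving q = 0.103 or 0.19. Assume match probabilities of 0.70 (higher literacy) and 0.10 (low), and let k be the ratio of AVI receipt, low to higher literacy, among controls.

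- Low-literacy share among control recipients: s = qk / (qk + 1 − q)
- Match rate: 0.70 − 0.60q in a fully scored AVI arm; 0.70 − 0.60s among scored controls

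| q | k | s | AVI arm | Scored controls | Difference (points) |
|---|---|---|---|---|---|
| 0.103 | 0.5 | 0.054 | 0.638 | 0.667 | −2.9 |
| 0.103 | 1 | 0.103 | 0.638 | 0.638 | 0 |
| 0.103 | 2 | 0.187 | 0.638 | 0.588 | +5.0 |
| 0.19 | 0.5 | 0.105 | 0.586 | 0.637 | −5.1 |
| 0.19 | 1 | 0.190 | 0.586 | 0.586 | 0 |
| 0.19 | 2 | 0.319 | 0.586 | 0.508 | +7.8 |

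With other assumed inputs (match 0.90 and 0.20; receipt between 30% and 90%, differing by literacy) the range widens to −8.2 to +15.6 points. Everything except q is assumed. Neither sign nor size follows from the documents, and zero is as admissible as any other value.

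**4. Would a different analysis do better?**

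- *Count no AVI as not matched, over all randomised patients.* With identical writing (assumed 60% match) and full delivery in the AVI arms, the comparison is 0.60 against 0.60r, that is 0.12, 0.24 or 0.36. The gap of 48, 36 or 24 points comes from delivery alone, which the intervention mandates. It says nothing about readability.
- *Compare only the two AVI arms.* Both use the same template, so this addresses teach back and not the template. It also needs near-complete delivery. With delivery d in both arms and equal match among recipients, the difference is uncertain by ±(1 − d), or ±10 points at d = 0.90. If recipients' match is 70% and 50%, the full-arm rates lie in 0.63 to 0.73 and 0.45 to 0.55. The full-arm difference is then 8 to 28 points against 20 observed, a shift of −12 to +8.

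**The case for a change.** The best case for a change is that the outcome belongs to a three-arm randomised trial. Tables are promised for all variables, and setting them out by arm is the natural way to present them. Once that is done, readers will compare columns whether or not a test is written. The retrospective finding gives limited comfort: it concerns medications, comorbidity and learning preference, and as described it is silent on literacy and on provider, the two factors most likely to matter here. A sentence or two on denominators would cost little.

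Much of this stands. A contrast between controls and AVI recipients would lack the protection of randomisation, and it should not be presented as the template's effect. But this is a caution about reading a comparison the plan does not state. The lack of AVI among controls is itself an inference from past practice. Providers are now trained in the template, so past use may not carry over, and if the after-visit summary were counted as an AVI the gap could shrink or close. All patients also complete a post-visit survey that asks how AVI were implemented. Its items are not shown, so it may not record receipt, but some information on provision is planned in every group.

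**Conclusion.** No change follows. The point about conditioning on receipt is correct in principle, but it bears on an analysis the plan does not contain. Followed as written, the plan yields a sound description of how AVI provided fit their readers. What is missing is reporting detail that an analyst would supply as routine: say what was counted as an AVI, show by arm how many were randomised, given an AVI and scored, and treat any contrast with controls as descriptive. The alternatives either measure delivery or answer a different question.

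No size can be attached to the concern. That some controls will have no value is probable but inferred, and every receipt and match rate above is assumed for a match the documents do not define. The conclusion rests on the literacy outcome remaining a description. If a report claimed from it that the template improved readability over usual care, the caution would apply in full. Retention and satisfaction are collected in all groups and are not touched.

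### Does deleting all data at an undefined study completion put a secondary outcome, or later follow-up, at risk?

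*Combined protocol and SAP*

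**What the plan says.** The combined protocol and SAP touches on this point in five places.

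- **Section 6, Data Management**, closes with "All data will be deleted at the completion of the study". It gives no date, trigger event or retention period, and exempts nothing. The data are coded: "Those that have access to the coded data will require a key to interpret the data". No separate rule covers the key.
- **Section 5, Procedures Involved**, ends with the readability work: "After the study, AVI provided will be assessed using Flesch-Kincaid Readability Scores and Grade levels to see how they correspond to patients baseline literacy".
- **Section 2, Objectives**, names one primary outcome (retention, from the telephone call) and two secondary outcomes. The secondary outcomes are patient satisfaction and "after visit instructions meeting patients' health literacy levels measured from the REALM-A".
- **Section 3, Background**, looks ahead: "Long-term studies will analyze how these interventions may have impacted various health related outcomes and patient reported outcomes". The last patient contact in this trial is far earlier: "Within 1-2 weeks after the patient's initial visit, a standardized phone call will be performed".
- **Section 7, Risks/Benefits**, gives the main risk as one to subjects' "confidentiality should an individual outside of the study team access the study data".

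**The concern.** Deletion cannot be undone, and here its trigger is a term the plan never defines. If *the study* means the same thing in Sections 5 and 6, the data go when the study ends and the readability comparison comes afterwards. The AVI texts might survive in the electronic record, where providers find the templates. The REALM-A scores are described only as a form completed for this trial, and linking the two needs the key. A named secondary outcome could then become impossible to analyse.

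A second worry is that the long-term work in the Background might need the randomised allocation and the key, which the rule would have destroyed. A third is that nobody could re-check the retention scores once the data are gone.

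**Working it through.** The plan states no sample size, power or error rate that bears on this point, so there is no figure to reproduce. The check is to compare the passages and count the outcomes lost under each possible reading.

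**Inputs.** Section 2 gives 1 primary + 2 secondary = 3 named outcomes. The plan sets no date for any analysis. The only marker is that the readability assessment comes *after the study*.

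**Outcomes lost under each reading**

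| Meaning of *the study* | Deletion occurs | Outcomes lost |
|---|---|---|
| Patient contact only, in both sections | after the last call, before any final analysis | 3 of 3 |
| Patient contact in Section 5; the whole project, with analyses, in Section 6 | after all analyses | 0 of 3 |
| Contact plus analysis of retention and satisfaction, but not readability, in both sections | between those analyses and the readability work | 1 of 3 (1 of 2 secondary) |

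**Which reading fits the text**

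1. The first would erase the primary outcome before it was analysed. It also contradicts Section 6 itself, which stores the coded data for analysis and promises summary tables for every variable. Nobody would carry it out.
2. The third is the only one that loses exactly one outcome. It needs a study that includes two of its outcomes and leaves out the third, although Section 2 lists all three together. No section draws that line.
3. The second fits every passage. Section 5 runs through the visit, the forms, the telephone call at 1-2 weeks (7-14 days) and baseline collection, then turns to readability. In that position, *after the study* means after the patient procedures. In Section 6, deletion is the last step, following tabulation and storage for analysis. Completion there is the end of the work, including the outcome defined by "health literacy levels measured from the REALM-A".

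**Long-term studies.** The Background paragraph first describes what this study will do and then speaks of other studies, in the plural. Sections 2 and 5 contain no long-term outcome, and no section says the later work would use these participants, this dataset or this key. The deletion rule could block that work only if it did.

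**Effect on results.** On the second reading the primary estimate, both secondary analyses and any checks made before deletion are the same whether the term is defined or not.

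**The case for a change.** The strongest reply is that an irreversible step should not rest on inference. The plan uses *the study* in Section 5 for something that ends before an analysis, and shortly afterwards ties deletion to the end of *the study*. A data manager who took both literally would have grounds for acting too soon. Even on the benign reading no coded dataset survives, so the retention score, which is the primary outcome and depends on the study team's scoring of telephone answers, could never be re-checked.

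Two parts of this stand. The term is undefined, and one clause would settle it. The loss of later re-checking is real on any reading.

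Neither part makes the plan wrong. Acting on the literal wording would mean deleting data while a listed outcome was still open, and the team that wants that result also controls the deletion. Keeping a coded dataset, or the key, would change no estimate or conclusion of this trial. It would lengthen exposure to the risk that Section 7 ranks first, with coded data held on laptops under Section 9. What participants were told about retention is in a consent form that is not part of the available text, so a reviewer has no basis for reversing the rule.

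**Conclusion.** The concern does not call for a change. The undefined word is a gap that analysts fill sensibly: deletion follows all analyses named in the protocol, including AVI readability against REALM-A. On that reading 0 of 3 outcomes is lost and the primary estimate is unaffected. The loss of 1 of 2 secondary outcomes arises only under a definition the plan does not contain, so it should not be cited as a measure of harm. The long-term studies create no conflict on the text as written.

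Full deletion, with no later re-checking, is a fair trade-off against the protocol's own main risk. A clarifying clause would do no harm if the document were amended for another reason, but no result depends on it.

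This rests on two assumptions: that the study team treats a study with an unassessed outcome as incomplete, and that the long-term studies are separate projects. If the sponsor does intend to follow these same participants by randomised group, retention of the allocation and key would have to be looked at again together with the consent form.
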